2.9 PD and PK/PD analyses

[figure not shown]
The relationship between PK (CFZ533 concentration in plasma; Section 2.8) and PD (total soluble CD40 in plasma; target engagement) will be explored graphically. All participants with evaluable PK and PD parameters will be included in the data analysis.

Total soluble CD40 for all participants in the PKS will be listed by treatment, participant, and visit/sampling time point. Total soluble CD40 concentrations will be given in mass per volume units (in nanogram/mL). Descriptive summary statistics will be provided by treatment and visit/sampling time point, including the frequency (n, %) of concentrations below the LLOQ. Summary statistics will include mean (arithmetic and geometric), SD, CV (arithmetic and geometric), median, minimum, and maximum. Concentrations below LLOQ will be treated as zero in summary statistics. A geometric mean will not be reported if the dataset includes zero values.

The zz.xpt file in GPSII will combine PK data (free CFZ533 in plasma) as well as sCD40 data in plasma (PD) (Section 2.8).

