8.5.2 Pharmacokinetics

Free CFZ533 plasma concentrations will be measured in all CFZ533-treated participants (Arms 2 and 3 only).

All blood samples will be taken by either direct venipuncture or an indwelling cannula inserted in a forearm vein (opposite to the site of the IV administration on Day 8 or Day 15). Details of sample processing, handling, storage and shipment will be described in a separate laboratory manual. All samples will be given a unique sample and collection number. The actual sample collection date and time will be entered on the appropriate CRF.

Free CFZ533 plasma concentrations will be determined using a validated target-based sandwich enzyme-linked immunosorbent assay (ELISA) method. The lower limit of quantification (LLOQ) is 0.03 μ g/mL in 100% human plasma. The data and details of the analytical methods will be provided in a standalone Bioanalytical Data Report. Concentrations below the LLOQ will be reported as "zero" and missing data will be labeled as such in the Bioanalytical Data Report.

For standard pharmacokinetic abbreviations and definitions see the list provided at the beginning of this protocol.

The following PK parameters will be determined: Ctrough at steady state and Cmax will be directly derived from the bioanalytical data and listings. Additional PK parameters may be determined if data permit.

No other parameters (e.g. clearance, volume of distribution, or half-life) will be derived using non-compartmental analysis (NCA). The pharmacokinetics of CFZ533 is non-linear and characterized by target-mediated disposition where CD40 binding by CFZ533 is leading to

CFZ533 elimination (this includes receptor-mediated endocytosis by the membrane bound CD40, and subsequent metabolism of the CFZ533-CD40 complexes). As such, it is expected that:

- The amount of drug-target complex does influence the pharmacokinetics of CFZ533,
- Tissue metabolism may have a significant impact on the disposition of CFZ533 (the volume of distribution will be dependent on clearance),
- The volume of distribution may not be accurately inferred from plasma concentration alone, and the values for the volume of distribution obtained from a NCA may be incorrect,
- Volume of distribution and clearance parameters (as inferred from NCA analysis) would decrease when the dose increases.

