• To assess the levels of peripheral soluble CD40 at baseline and over the 12-month and 24-month treatment period (to inform target biology, target engagement).	• Total sCD40 in plasma (all participants).
 To evaluate the immunogenicity of CFZ533 by analysis of anti-CFZ533 antibodies (over the 12- month and 24-month treatment period). 	 Semi-quantitative analysis of anti-CFZ533 antibodies in plasma (CFZ533-treated participants only).

2 Statistical methods

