2.1.2 Analysis sets

The screened set (SCR) consists of all participants who signed the informed consent. The screened set includes only uniquely screened participants, i.e., in the case of re-screened participants, only the chronologically last screened data is counted. Screening phase disposition will be based on the SCR.

The randomized set (RND) consists of all participants who signed the informed consent and were randomized, including misrandomizations.

The full analysis set (FAS) will include all participants who were transplanted and randomized, excluding mis-randomized participants. Mis-randomized participants are defined as cases where IRT contacts were made by the Investigator/qualified site staff either prematurely or inappropriately to confirmation of the participant's final randomization eligibility and treatment was not administered to the participant. Following the intention-to-treat (ITT) principle, participants will be analyzed according to their treatment assignment at randomization. Participant demographics, baseline characteristics, efficacy and renal function measured by GFR will be performed on the FAS.

The safety set (SAF) consists of all participants in FAS who received at least one dose of study drug (i.e., at least one dose of TAC after randomization in the Control arm and at least one dose of CFZ533 in the CFZ533 arms). Participants will be analyzed according to the treatment they actually received. All safety analyses, including renal function parameters other than GFR, will be performed on the SAF using on-treatment (between start and end of treatment defined in Section 2.1.1) data unless otherwise specified.

The PK analysis set (PKS) will include all participants with at least one available valid (i.e., not flagged for exclusion) PK concentration measurement, who received any study drug and with no protocol deviations that impact on PK data, e.g. if a dose was taken more than 7 days after the planned date.

The total screened participants and each analysis population above will be summarized in terms of the frequencies and percentages. Listings of randomized participants and of the participants excluded from analysis sets will be provided.

Rules for exclusion from analysis sets is in Table 5-9.

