2.8 Pharmacokinetic endpoints

CFZ533 plasma concentration data will be listed by treatment, participant, and visit/sampling time point using PKS. Concentrations will be given in mass per volume units. Descriptive summary statistics will be provided by treatment and visit/sampling time point, including the frequency (n, %) of concentrations below the LLOQ.

Summary statistics will include mean (arithmetic and geometric), SD, CV (arithmetic and geometric), median, minimum, maximum, and 25% and 75% percentiles. Concentrations below LLOQ will be treated as zero in summary statistics. A geometric mean will not be reported if the dataset includes zero values. Summary statistics and graphical analysis (e.g., box plot) will

be provided to compare steady-state PK before and after introduction of PFS in the study. PK is considered steady after 10 weeks since PFS introduction.

If data permit, PK parameters will be calculated as described in Section 8.5.2 in Protocol and will be listed by treatment and participant. Descriptive summary statistics will include mean (arithmetic and geometric), SD, CV (arithmetic and geometric), median, minimum, maximum, and 25% and 75% percentiles.

In addition, CFZ533 concentration will be measured in any collected/drained ascites. The detailed methods and analysis will be described in the Bioanalytical Data Report.

In the zz.xpt file in GPSII (merge file), PK concentration (free CFZ533 in plasma) will be expressed in unit 'microgram/mL' (in addition to 'nanogram/mL'), and time will be expressed in unit 'day' (in addition to 'hours').

- a. Two variables for the elapsed time (*e.g.* EACLTM_1 and EACLTM_2) will be provided: elapsed time since first dose: EACLTM_1 is calculated using the Dose Reference ID provided in the Blood Log under Dose Reference ID series #1,
- b. EACLTM_2 is calculated using using the Dose Reference ID provided in the Blood Log under Dose Reference ID series #2; e.g. for Arm 2 (600 mg Q2W regimen) a Dose Reference ID of 17 for pre-dose PK Sample 115 on Day 225 (17ith dose of CFZ533) means that the elapsed time is calculated with reference to timing of 17ith dose of CFZ533 (and is negative).

The zz.xpt file in GPSII will combine PK data (free CFZ533 in plasma) as well as sCD40 data in plasma (PD). Similar to PK output, elapsed time variables (EACLTM_1 and EACLTM_2) will be generated.

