5.6 Rule of exclusion criteria of analysis sets

Table 5-9_displays the criteria for exclusions from analysis sets.

Table 5-9	Participant Classification		
Analysis Set	PD ID that cause participants to be excluded	Non-PD criteria that cause participants to be excluded	
SCR	INCL01	Not having informed consent;	
		Not having screening epoch disposition page	
FAS	INC03, OTH03, OTH10	Not randomized; Not transplanted;	
		Mis-randomized	
SAF	NA	No study drug taken	

Analysis Set	PD ID that cause participants to be excluded	Non-PD criteria that cause participants to be excluded
РК	NA	No study drug taken; PD with relevant impact on PK; no valid PK concentration measurement

6 Reference

Garwood, F (1936). Fiducial limits for the Poisson distribution. Biometrika, 46; 441–453.

Sahai H, Khurshid Anwer (1993). Confidence intervals for the mean of a poisson distribution: a review. Biom J, 35 (7); 857-867

Ulm K (1990). A simple method to calculate the confidence interval of a standard mortality ratio. American Journal of Epidemiology, 131(2); 373-375

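### SAP 2.9 lists soluble CD40 in the PK analysis set, which no tacrolimus-treated control participant can enter, although SAP Table 1-1 defines the endpoint for all participants

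*SAP*

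**What the plan says.** SAP Section 2.9 covers PD and PK/PD analyses together. It opens with a graphical exploration of CFZ533 concentration against total sCD40 and sets the population for it: "All participants with evaluable PK and PD parameters will be included in the data analysis". It then turns to sCD40 as an outcome in its own right: "Total soluble CD40 for all participants in the PKS will be listed by treatment, participant, and visit/sampling time point". After a note on units comes the summary sentence: "Descriptive summary statistics will be provided by treatment and visit/sampling time point". That sentence names no analysis set.

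SAP 2.1.2 defines the PKS as "participants with at least one available valid (i.e., not flagged for exclusion) PK concentration measurement", with the further conditions that the participant received any study drug and had no protocol deviation affecting PK data. SAP Table 5-9 excludes from the PK set anyone with "no valid PK concentration measurement".

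SAP Table 1-1 gives the endpoint for the sCD40 objective as "Total sCD40 in plasma (all participants", with the bracket closing there. In the same table the PK and immunogenicity endpoints are expressly limited to CFZ533-treated participants.

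**The concern.** Two parts of one SAP give different populations for the same secondary endpoint. The objectives table says everyone. The analysis section uses a set whose entry condition only CFZ533-treated participants can meet. A programmer who follows SAP 2.9 literally would produce an sCD40 listing without the control arm.

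The objective is to inform target biology and target engagement. Arm 1 is the only randomised arm without CFZ533, so it is the only concurrent reference for how sCD40 behaves after transplantation when CD40 is not blocked. Leaving it out removes that comparison from the report, although the samples are scheduled and assayed.

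**Working it through.** This is a check of definitions, followed by simple counts. The plan states no figure to reproduce.

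**Can a control participant enter the PKS?**

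1. SAP 2.9 draws the sCD40 listing from the PKS.
2. SAP 2.1.2 and Table 5-9 make a valid PK concentration a condition of entry.
3. SAP 2.8 identifies the analyte: "PK concentration (free CFZ533 in plasma", again with the bracket closing there.
4. Protocol 8.5.2 says who is assayed: "Free CFZ533 plasma concentrations will be measured in all CFZ533-treated participants", and adds that this means Arms 2 and 3 only.
5. Protocol Appendix 6a gives Arm 1 its own blood log. It has sCD40 samples numbered 400 to 412 and no PK column. The Arm 2 and Arm 3 logs have both.

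A tacrolimus-treated control participant therefore has no PK concentration and cannot be in the PKS. Tacrolimus and MMF trough levels do not change this. The assessment schedule carries them as separate rows, and both documents define PK in this study as free CFZ533.

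**Should control participants be reported?**

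- SAP Table 1-1 says all participants for sCD40, and it does limit the PK and immunogenicity rows where a limit is meant.
- Protocol Table 8-1, footnote 6, and Protocol 8.5.3 collect sCD40 in all arms, control included, and state that all samples are analysed.
- SAP 2.1.1 says outputs will display TAC + MMF as one of the three treatments.

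The protocol shows only that control samples are drawn and assayed. Its visible statistical section (12.5.4) plans just the graphical PK/sCD40 exploration. The inconsistency therefore lies inside the SAP.

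**The summaries.** There are two readings. If the summary sentence carries over the PKS from the listing sentence, the control column is empty. If it uses some other set, that set is not named and the listing does not cover the data summarised. Either way SAP 2.9 needs a correction.

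**Scale at planned size.** Inputs: 32 control participants of 128 (Protocol 6.1.3 and Section 3). The Arm 1 log in Appendix 6a has sampling on Days 8, 29, 57, 85, 127, 169, 225, 281, 337, 421, 505, 589 and 673, which is 13 time points. Nine of them fall by Month 12 (Day 337). Day 127 (Month 4.5) is not mandatory for Arm 1 under Protocol 8.5.3.

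- Share of participants: 32 / 128 = 25%.

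| Scheduled control samples | With Month 4.5 | Without Month 4.5 |
|---|---|---|
| Through Month 24 | 32 × 13 = 416 | 32 × 12 = 384 |
| Through Month 12 | 32 × 9 = 288 | 32 × 8 = 256 |
| Through Month 24, without Day 8 | 32 × 12 = 384 | 32 × 11 = 352 |
| Through Month 12, without Day 8 | 32 × 8 = 256 | 32 × 7 = 224 |

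The rows without Day 8 apply if the pre-treatment sample is assayed as free rather than total sCD40, as Protocol 8.5.3 suggests.

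**The case against.** The strongest counter-argument is that Table 1-1 is a poor guide to what this SAP will report. The study was terminated early. SAP Sections 1 and 2.1 say that analyses were reduced or modified for an abbreviated report, and the table was not trimmed to match. It still carries the secondary efficacy endpoints that SAP 2.6 removes, and it still carries means and mean changes of vital signs although SAP 2.7.4.3 plans only a listing. On this view the mismatch is a leftover. The restriction to participants with PK data may also be deliberate: Section 2.9 treats total sCD40 as target engagement, and SAP 2.8 gives it the same dose-referenced time variables as PK, which the Arm 1 log cannot supply.

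Part of this stands. Table 1-1 is untrimmed elsewhere, and the vital-signs example shows that this SAP sometimes narrows an output without announcing it. An intended restriction is therefore possible. But no text says that control sCD40 was dropped. SAP 2.6 shows that the document can state a removal when it makes one, and SAP Section 4, on changes to protocol-specified analyses, reads as not applicable. The plots already have their own population rule, so they do not need the PKS wording in the listing sentence.

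It is also fair that only the listing sentence names the PKS, that the endpoint has no test or decision rule, and that the sample counts are planned maxima. These points limit the weight of the finding but do not remove the contradiction.

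**Conclusion.** The concern holds. As written, the sCD40 listing omits every tacrolimus-treated control participant from an endpoint that the same SAP defines for all participants. This follows from the definitions and is certain for the listing. For the summaries it is the natural reading, not a stated one.

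At planned size the omission is 32 of 128 participants (25%) and up to 384 to 416 scheduled control samples through Month 24, or 256 to 288 through Month 12. Those ranges fall to 352 to 384 and 224 to 256 if Day 8 is assayed as free sCD40. All assume full enrolment and retention. The documents do not give realised numbers after early termination.

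The consequence is limited. The data would still exist, since the samples are assayed and the merged PK/sCD40 file in SAP 2.8 and 2.9 is not stated to be limited to the PKS. They would simply not be reported under SAP 2.9. The primary and key secondary analyses do not depend on this endpoint. It should be corrected, but it does not threaten the trial's main conclusions.

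**What to change.** In SAP 2.9, name one analysis set that includes the control arm and apply it to both the sCD40 listing and the by-treatment summaries. Safety Set participants with at least one sCD40 value would serve. Keep the requirement for evaluable PK and PD data for the PK/PD plots only.

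If leaving out control is intended, state that in SAP 2.9 and change the sCD40 row of Table 1-1 to match.

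The cost is one or two sentences, and the sCD40 listing and summary tables run on a different set. No new visits or samples are needed, because Arm 1 sCD40 sampling is already scheduled.

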2.10 Participant-reported outcomes

Not applicable.

2.13 Interim analysis

An interim analysis is planned after 80% participants have reached the Month 6 visit (or have prematurely discontinued the study before Month 6) where all endpoints are analyzed as in the full CSR using on-treatment data with exceptions as described below.

Efficacy data of all participants available at the cutoff date, including data beyond Month 6 and participants not yet reaching Month 6, will be included. The primary endpoint (the composite efficacy failure rate) will be analyzed based on a Poisson model to adjust for different follow-up time of participants at the cutoff date (see Section 2.4.4 for details). Other primary comparisons not using Poisson model, including the key secondary endpoint will be based on data up to Month 6

visits to maximize the sample size. All summaries by visits will include all visits, including those beyond Month 6. Safety analyses, including AE, SAE, infections, serious infections, death, and safety topics of interests, will be analyzed for participants who complete Month 6 and for all participants based on exposure adjusted rates, respectively.

The primary objective of the interim analysis is to enable the overall benefit-risk assessment. There are no plans to stop the study early for good efficacy, since it is desired to collect longterm efficacy and safety data.

3 Sample size calculation

3.1 Study stopping rules

The stopping rules will be evaluated by the clinical team and the DMC will review data at regular intervals as described in the Section 10.2 in the Protocol and the DMC charter. In case the stopping rule is reached for a treatment arm, recruitment to that arm will be stopped and all available data reviewed. The decision to continue or permanently stop the treatment arm or adjust study procedures will be taken based on a thorough evaluation of the available data.

Stopping rules for the incidence of centrally read moderate to severe BPARs (RAI \ge 6) and serious infections will be applied. These rules are designed to ensure that they trigger if there is high probability (>90%) that the true BPAR or serious infection rate is greater than 20%. In other words, a trial is to be stopped if:

$$P(\theta_i > 0.2 | \text{data}) > 0.9,$$

where θ_i is referring to the event rate of arm *i*, and the prior is Beta(1/3, 1/3).

Based on these stopping rules and depending on the number of participants randomized to a treatment arm at a given point in time, the number of participants that experienced a BPAR or a serious infection in this arm that would first trigger the stopping criterion are given in Table 3-1.

Number of participants randomized to the treatment arm (N)	Number of participants with observed event in the treatment arm that would lead to stopping the treatment arm (n)	Observed event rate (n/N)
3	2	67%
4	2	50%
5	3	60%
6	3	50%
7	3	43%
8	4	50%
9	4	44%
10	4	40%
11	5	45%
12	5	42%
13	5	38%
14	5	36%
15	6	40%
16	6	38%
17	6	35%
18	6	33%
19	7	37%
20	7	35%
21	7	33%

Table 3-1Stopping rules per number of events

Novartis	5
SAP	

[figure not shown]
Number of participants randomized to the treatment arm (N)	Number of participants with observed event in the treatment arm that would lead to stopping the treatment arm (n)	Observed event rate (n/N)
22	7	32%
23	8	35%
24	8	33%
25	8	32%
26	8	31%
27	9	33%
28	9	32%
29	9	31%
30	9	30%
31	10	32%
32	10	31%
33	10	30%
34	10	29%
35	11	31%
36	11	31%
37	11	30%
38	11	29%
39	12	31%
40	12	30%
41	12	29%
42	12	29%
43	13	30%
44	13	30%
45	13	29%
46	13	28%
47	14	30%
48	14	29%

Properties of stopping rule

The stopping rules as defined in Section 3.1 are designed to ensure that enrollment in a treatment arm will be stopped if there is a high probability (>90%) that the true BPAR or serious infection rate is greater than 20%.

Figure 3-1 indicates the probability of stopping enrollment in a treatment arm for various true BPAR or serious infection rates. The thresholds for the stopping rules ensure that the chance of stopping enrollment in an arm is sufficiently high for true high BPAR or serious infection rates, while remaining appropriately low when the true rates are low.

Figure 3-1 Probability of stopping a cohort for various event rates for up to 48 participants per arm

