9.1.5 Study stopping rules

Until Month 24, stopping rules for the incidence of BPAR and serious infections will be applied. These rules are designed to ensure that they trigger if there is high probability (>90%) that the true BPAR (RAI \geq 6, evaluated by central reader) or serious infection rate is greater than 20%.

Novartis	Confidential	Page 100 of 136
Amended Clinical Trial Protocol (Version No.	04 clean)	Protocol No. CCFZ533A2202

Infections declared as "Life-threatening" by the investigator or with fatal outcome will be considered as serious infections for the purpose of this stopping rule.

Based on this stopping rule and depending on the number of participants randomized to a treatment arm at a given point in time, the number of participants that experienced a BPAR or a serious infection in this arm that would first trigger the stopping criterion are given in Table 12-1.

In case the stopping rule is reached for a treatment arm, recruitment to that arm will be stopped and all available data reviewed. The decision to continue or permanently stop the treatment arm or adjust study procedures will be taken based on a thorough evaluation of the available data.

No stopping rules will be assessed during the long-term extension.

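### The stopping rule counts everyone randomised as fully observed, so during accrual it understates the posterior probability and triggers later than its boundaries imply

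*SAP*

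**What the plan says.** SAP 3.1 stops an arm when P(θ > 0.2 | data) exceeds 0.9, under a Beta(1/3, 1/3) prior. It applies this separately to centrally read moderate-to-severe rejection and to serious infection. Table 3-1 turns the criterion into event counts for N = 3 to 48, where N is the number randomised to the arm. The threshold is set "depending on the number of participants randomized to a treatment arm at a given point in time", and each entry is the count that "would first trigger the stopping criterion". When it is reached, "recruitment to that arm will be stopped and all available data reviewed".

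Protocol 9.1.5 repeats the rule and gives its duration: "Until Month 24, stopping rules for the incidence of BPAR and serious infections will be applied". Protocol 6.4 says the sponsor team assesses it on real-time unblinded data.

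On performance, the SAP says that the thresholds "ensure that the chance of stopping enrollment in an arm is sufficiently high for true high BPAR or serious infection rates". The readable text gives no figure for that chance. Figure 3-1 is not shown, and Protocol Section 12.6 and Table 12-1 are not in the text available, so nothing is held against the plan on their account. The readable text sets no minimum follow-up, no exposure adjustment and no time horizon for the 20% rate.

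**The concern.** A binomial likelihood needs a known outcome for each of the N participants. Here N includes people whose observation has barely begun, and each adds one full event-free observation to the denominator. While an arm is enrolling, the calculated value is therefore lower than the probability the SAP says it is, and the number of events needed rises with each randomisation rather than with information gained.

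Rejections and serious infections accrue over months while recruitment continues. A rule meant to halt enrolment in a poor arm may then be reached late in accrual, or only after accrual has closed, when it can no longer limit how many people enter that arm. Protocol 4.6 and 4.7 cite these rules as a way of limiting risk, in what Protocol 1.1 describes as the first liver-transplant study of this drug.

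**Working it through.** **1. Reproduce Table 3-1.** With n events in N, the posterior is Beta(1/3 + n, 1/3 + N − n). The threshold is the smallest n with P(θ > 0.2) > 0.9. All 46 entries match exactly. For example, 2/4 gives 0.915 and 2/5 gives 0.853, so the table moves from 2 to 3. Likewise 7/22 gives 0.905 and 7/23 gives 0.883, so it moves from 7 to 8. Beta(1,1) and Beta(0.5,0.5) do not reproduce the table. The boundaries are therefore plain beta-binomial, with no allowance for follow-up.

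**2. Effect of unobserved participants.** Suppose 24 participants have been followed and 8 have had events. The posterior is 0.938 and the boundary is met. Now suppose others had already been randomised, with no follow-up, when the eighth event occurred:

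| N counted | 24 | 27 | 30 | 36 | 48 |
|---|---|---|---|---|---|
| P(θ > 0.2), 8 events | 0.938 | 0.884 | 0.812 | 0.630 | 0.277 |

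The evidence about θ is the same in every column. At N = 36 the table asks for 11 events instead of 8.

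**3. What the boundaries give with immediate outcomes.** An exact sequential binomial calculation up to N = 48 gives a chance of triggering of 0.07, 0.38, 0.83 and 0.99 at true rates of 10%, 20%, 30% and 40%.

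**4. Accrual.** The Protocol reports 20 randomised by 30 July 2020 and 59 by 28 February 2021: 39 in 7 months, or 39/7 = 5.6 per month. At 2:3:3 allocation each CFZ533 arm receives 5.6 × 3/8 = 2.1 per month, and 48/2.1 is about 23 months. A range of 18 to 30 months brackets this. The fast end is optimistic, since 59 of 128 had been randomised about 18 months after the September 2019 start.

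**5. Staggered entry, rule as written.** Assumptions not in the documents: 48 per arm, monthly looks, and two event-timing patterns (constant hazard; 75% of events in the first 3 months).

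| True rate | Immediate outcomes | Triggered during accrual | Triggered at any time |
|---|---|---|---|
| 30% | 83% | 17–38% (constant hazard); 44–64% (early events) | 61–70% |
| 40% | 99% | 49–92% (both patterns) | 95–98% |

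These are simulation results and move by several points with modelling detail, so they should be read as ranges.

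**6. Why it is mainly delay.** Once all 48 are fully observed the rule needs 14 events. P(X ≥ 14) for Binomial(48, p) is 0.604 at p = 0.30 and 0.956 at p = 0.40, which is the floor for an eventual trigger.

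**7. Does real-time checking rescue it?** At 2.1 per month and a true 30%, continuous checks give a trigger during accrual in 0.28 (events uniform over 12 months) or 0.58 (75% early). Six-monthly checks give 0.14 or 0.40. Mean enrolment under continuous checks is 43.7 or 33.8, against 18.8 with immediate outcomes. If events were spread evenly over 24 months, the continuous-check figure would be 0.02, so the undefined time horizon matters.

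**The case against.** Several points on the other side stand.

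- **Un-triggering.** A reader might infer from the arithmetic that new enrolment can reverse a trigger. If the rule is assessed in real time and recruitment stops when the boundary is first reached, N in that arm cannot then grow. Reversal is possible only with periodic checks or late central biopsy readings. The documents do not say whether a trigger, once reached, persists in those cases.
- **A broken numerical promise.** A reader might take 90% as the chance of stopping a bad arm. It is a posterior threshold. With Figure 3-1 not shown, the rule cannot be said to miss a stated figure. The 83% comparator is computed from Table 3-1's boundaries and is not quoted from the plan.
- **Later detection.** The rule runs to Month 24, and a late trigger still prompts review and possible closure of the arm. It cannot, however, stop enrolment that has already finished.
- **Event timing.** Protocol 4.2.1 notes that, with another anti-CD40 antibody in kidney transplantation, most rejections in the CNI-free arm occurred before Day 60. That makes the early-event results plausible. They are better than under constant hazard but still well below 83% at a true 30%.
- **Other safeguards.** The DMC meets about every 6 months, and the interim analysis uses a Poisson model to adjust for unequal follow-up, so this rule is not the only protection. The interim analysis also shows that the plan accepts the need for adjustment, which the stopping rule omits.
- **Timing of this SAP.** It postdates the September 2022 termination, so a change cannot alter conduct. Section 3.1 still asserts these properties.

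**Conclusion.** The denominator defect is in the text and does not depend on simulation: during accrual the rule computes a value below the posterior probability it is said to represent, and it triggers late. The size does depend on assumed accrual, look frequency and event timing. At a true 30% rate, the chance of triggering while enrolment is open falls from 83% to somewhere between about 17% and 64%.

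It would be too strong to conclude that a bad arm usually escapes. At a true 40% the rule still triggers during accrual in about half to nine-tenths of trials and almost always does so eventually. The supported conclusion is delay, with more participants enrolled before review, and an assurance about stopping enrolment that is not secured under staggered entry.

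**What to change.** Keep the Beta(1/3, 1/3) prior and the 20% and 90% thresholds, and make four changes in SAP 3.1 and Protocol 9.1.5:

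1. State the period over which the 20% rate is defined.
2. Apply the Table 3-1 boundaries to participants with a fixed minimum follow-up, for example 3 months. Run this alongside the existing count on all randomised, so that early events in recent enrolees are not dropped.
3. State that a reached trigger stays in force when checks are periodic or central readings arrive late.
4. Recompute Figure 3-1 under staggered entry for a range of accrual rates and event timings.

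Under the same assumptions, a 3-month minimum raises triggering at a true 30% to about 35–72%. The cost is more reviews near the threshold: about 4–29% at a true 20%, still below the 38% the boundaries give with immediate outcomes, and at most 3.5% at a true 10%. A trigger pauses recruitment to that arm for data review; it does not end the arm automatically.

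Weighting event-free participants linearly over 12 months is not advised unless the weights match event timing. With early events it triggers in 53–62% at a true 20% and about 20% at a true 10%.

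The work is a few sentences and a small simulation. As the trial has ended, its use is to qualify how the rule's performance is reported and to correct the rule before it is reused.
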